### 5.4 SCREEN FAILURES

Screen failures are defined as those individuals who consented to participate in the study, but who are subsequently deemed ineligible, usually after the screening visit urine analysis and culture.

Individuals who test positive for a UTI at their screening visit may be re-assessed for eligibility after prescribed antibiotic use. Individuals who undergo a second positive urine tests with UTI symptoms following treatment are ineligible for the study (i.e.; categorized as a screen failure).

Additionally, females of childbearing potential who have a positive screening pregnancy test will be categorized as a screen failure.

### 5.5 STRATEGIES FOR RECRUITMENT AND RETENTION

#### RECRUITMENT

This study will use a multi-pronged approach to recruitment that includes physician-referral, weekly reviews of the Michigan Medicine Urology and PM&R clinic schedules, use of MiChart Best Practice Alerts (BPAs) for satellite outpatient clinics, use of flyers for recruitment at clinics and community based agencies, use of UMhealthresearch.org (which may be linked to the patient's electronic health portal), the MSCIS database and UM SCI Research Registry, Neurogenic Bladder Clinical Database, Patient

Reported Outcomes for Bladder Management Strategies in Spinal Cord Injury project database, and outreach to other related databases and patient advocacy groups in Ann Arbor and surrounding locales. Key criteria for targeting appropriate individuals will include:

- Age
- Presence of SCI and neurogenic bladder (evidenced by neurological classification when possible)
- Use of CIC or catheterization through a stoma
- Experience with recurring documented UTIs (2 or more in the prior six months)
- Availability of regular physician for treatment of any UTIs who is affiliated with Michigan Medicine

The study team will pre-screen EMRs for pertinent eligibility criteria. The study team will also check individuals referred by physicians in clinic, or responses of patients to in-clinic flyers, for eligibility. Individuals meeting this first pass at eligibility can be contacted in multiple ways:

- Approached in clinic by a referring physician or by the study coordinator and/or her trained assistant.
- Sent an introductory letter about this trial.
- Contacted via email with the same information as contained in the introductory letter.

Interested individuals will be invited to a research interview at which time the consent dialog will be initiated and eligibility confirmed. This interview will be conducted through secure, encrypted video conferencing or over the phone.

- Individuals will be emailed a copy of the consent document and a study information sheet prior to the initial research interview. If the individuals do not have email access, physical copies will be mailed.
- Individuals will be invited to review the study information on UMhealthregistry.org prior to the initial research interview.
- We will suggest that the individual share their intentions about potential participation with their family, caregiver, regular physicians, and/or care team prior to the initial research interview.
- We anticipate the ability to screen at least 30-50 participants in order to obtain a sample of 25 potential participants following eligibility screening with the goal of enrolling and retaining a minimum of 15 participants..
- Special efforts will be made to recruit minority participants by ensuring that all potential eligible minority participants are contacted and invited to participate.

---

## RETENTION

The study team will strive for an empathetic relationship with participants to promote retention across their study participation period. Strategies for developing this type of relationship include:

- Minimizing distractions and interruptions during research encounters (visits, phone calls, etc.)
- Being present in the moment.
- Engaging in active listening.

- Being aware of non-verbal cues, i.e. body language, that may turn off an individual.
- Using teach-back methods of communication and information sharing to ensure mutual understanding.
- Keeping individuals updated and aware of necessary and useful information.
- Allowing individuals to correct or add to study team responses.
- Engaging on a personal level, when appropriate.
- Being culturally responsive and aware; assess personal implicit biases.
- Addressing questions participants may have about the study.

Study team members will implement the above strategies in all participant encounters whether planned or ad hoc. In addition to regularly scheduled research phone calls or e-visits for outcome assessments, participants will be contacted bi-weekly via phone calls. These bi-weekly encounters, while ostensibly for the primary purpose of collecting information about UTI occurrences, adverse events, and other symptoms, will also be used to maintain and promote an ongoing relationship with study participants, thus facilitating retention.

## REMUNERATION & INCENTIVES

Participants will be paid \$90 for participating in the study, \$30 at their baseline, six-month, and 3-month post-intervention assessments. Payments will be processed through the Human Subjects Incentive Program and will be conveyed via check or gift card. The precise method of payment will default to check, with the other option being offered upon request for a different method of remuneration.

### 6.1 STUDY INTERVENTION(S) ADMINISTRATION

*Section 6.1 makes repeated references to remote interviews, which will be conducted via an encrypted, HIPAA-compliant video conferencing platform (e.g., Zoom for Health.) It will be standard practice to conduct as many procedures remotely as possible to better protect subject/caregiver(s) and staff against the risk of COVID-19. However, in cases where a remote video interview is not possible, remote telephone interviews will be conducted and the study will follow all UM guidelines for proper consenting.*

#### 6.1.1 STUDY INTERVENTION DESCRIPTION

Eligible participants will be given the investigational product (gentamicin + saline solute). Those who use “a closed system” for catheterizing will also be provided with catheters to insert the investigational product into their bladders. Upon the termination of treatment, they will complete a study visit consisting of a blood draw, urine sample, and self-reported quality of life (QOL) measures. Additionally, a safety review will be conducted within 30 days after treatment termination by a member of the study team to assess for any adverse events. Approximately three months following the termination of treatment, participants will complete a final study visit to assess current Gentamicin use and UTI occurrences. Those interested will complete a brief survey about their perceptions of this treatment and

trial during or following the 3 months follow up. The treatment period lasts six months, beginning at the time of the first bladder instillation. Data collection will occur at baseline, at the biweekly visits, at the end of the treatment, and three-months post-treatment. Participants will be monitored bi-weekly throughout the trial through remote video interviews, and/or phone calls. The daily treatment consists of each participant and /or caregiver flushing the bladder with the treatment drug via bladder or stoma catheterization in the evening, leaving it in overnight, and emptying it the next morning.

### **Treatment**

Consists of Gentamicin, an aminoglycoside antibiotic indicated for a variety of gram-negative bacterial infections and saline. The drug will be sent by the Michigan Medicine Research Pharmacy in a concentration of 60mg of the active product to 50ml of normal saline. Participants will receive catheters and syringe tips and will withdraw 25ml with their syringe, switch tips, instill, and dispose of remaining 25ml of solution daily. Participants' shipments will be ordered every 28 days +/- 2 business days by the study team.

---

#### **6.1.2 DOSING AND ADMINISTRATION**

The study treatment will either be self-administered or administered by a caregiver. During treatment participants will be instructed to follow their normal catheter routine for bladder emptying at night, before bed. Once the bladder is empty, participants will attach the syringe containing the study product to the end of the catheter and slowly push the solution into the bladder. Once the full dose is instilled into the bladder, the participant will remove the catheter and syringe, leaving the study product in the bladder until the following morning. Participants will be asked to document the date and time of instillation and the date and time of bladder emptying the next morning in their daily dosing log, along with any other comments related to the process or related observed complications. In summary the process involves:

1. Emptying the bladder as usual at night, before bed
2. Attaching the catheter tip to the syringe
3. Flushing the bladder with the solution
4. Discarding the catheter tip and disposing of used syringe
5. Leaving the solution in place until next routine bladder emptying
6. Emptying the bladder with catheter as usual at next routine bladder emptying the next morning

#### **Treatment condition: gentamicin + saline**

- Instillation dose of 25mL solution every day; gentamicin dose = 30mg.
- Instillation to occur at night after the last bladder emptying of the day before bed.
- Self or caregiver administered via catheter.
- To remain in the bladder until next catheterization.

To ensure proper administration, participants and their caregivers will receive training on how to conduct the daily instillations. This training and printed information that includes contact information

for the study team will be provided to participants. A blank copy of the daily dosing log will be included as well. The process will also be explained to them when they enter the study.

## 6.2 PREPARATION/HANDLING/STORAGE/ACCOUNTABILITY

### 6.2.1 ACQUISITION AND ACCOUNTABILITY

Michigan Medicine Research Pharmacy will maintain study medication supply (both active and control products) and be responsible for dispensing the medication and study supplies (syringes, needles, catheter tips, and dosing logs) directly to the participant. Participants will receive their study medication in the mail via ground delivery. A signature at delivery is preferred. The Research Pharmacy will maintain shipping records and the study team will follow-up with participants to ensure receipt of study materials at the appropriate bi-weekly visit. The study participants will be asked to maintain a dosing log and review educational materials supplied by the study team. They are not required to save the used syringes but should refrain from re-using the syringes.

The Research Pharmacy and Study Team shall retain records of the following:

- Product shipped date.
- Product received date.
- Quantity of product shipped.
- Batch/serial numbers of products.
- Product expiration dates.
- Participant compliance.

The study team will call participants to confirm receipt of study product. Accommodations will be made for vacations and other travel away from home.

### 6.2.2 FORMULATION, APPEARANCE, PACKAGING, AND LABELING

The individual mini bags sent to participants will be labeled with study identification, participant identifier, a “use-by date”, and contact information for study team. A patient education sheet for drawing up and administering the irrigation solution will be included with the shipment. The immediate package shall bear a label with the statement “Caution: New Drug--Limited by Federal (or United States) law to investigational use.”

### 6.2.3 PRODUCT STORAGE AND STABILITY

Active products should be stored at room temperature in the packaging they were shipped in.

Participants will be instructed to contact the study team (who will contact the Research Pharmacy) in the event that: 1) they receive a damaged parcel or contents, 2) they notice anything unusual about the syringes or contents, and 3) if they failed to receive an expected delivery. Participants will be advised to look for:

- Signs of a mishandled opened parcel.
- Cracks or evidence of tampering with the mini bags.
- Distortions in the solution, e.g., cloudiness, particulates, etc.

#### 6.2.4 PREPARATION

The active study product (Gentamicin+ saline) will be obtained by the Research Pharmacy from Baxter. This is a premixed solution of 60mg of gentamicin in 0.9% NaCl 50 mL. Participants will be shipped parcels from the Research Pharmacy every 30 days +/- 2 business days. These parcels include the study product in a IVPB bag, IVPB solutions, 18 g 1.5 needles (boxes of 100), syringe catheter tip, alcohol swabs, and sharps container (for needles), sufficient to cover at least 28 days of treatment.

### 6.3 MEASURES TO MINIMIZE BIAS: RANDOMIZATION AND BLINDING

#### RANDOMIZATION

Not Applicable.

#### UN-BLINDING

Not Applicable.

### 6.4 STUDY INTERVENTION COMPLIANCE

Participants will be asked to complete a daily dosing log to promote and record compliance with the treatment protocol. The participants will share these logs during their 6-month outcome assessment. This will generally be done by emailing them to the Study Coordinator. Data captured will include dates and items of dosing, as well date and time of the subsequent catheterization (to estimate duration of instillation), and any challenges or problems encountered. Participants will be requested to return any unused investigational product to the study site at the end of the treatment period for disposal.

Additionally, the Study Coordinator will ask about compliance with the dosing protocol and study log completion, along with any barriers at the bi-weekly phone calls. The dates, times, and content of these calls will be documented in the study record.

### 6.5 CONCOMITANT THERAPY

For this protocol, a prescription medication is defined as a medication that can be prescribed only by a properly authorized/licensed clinician. Medications to be reported in the Case Report Form (CRF) are concomitant prescription medications, over-the-counter medications, and supplements.

During each bi-weekly call, participants will be asked about any changes in medications.. Changes will be entered into the CRF.

Concomitant use of ethacrynic acid and furosemide is not permitted in this protocol due to the increased risk of neurotoxicity. Additionally, concurrent use of systemic antibiotics for any reason is not permitted. Subjects prescribed a course of systemic antibiotic therapy will discontinue study treatment for the duration of their antibiotic course.

#### **6.5.1 RESCUE MEDICINE**

Participants experiencing a symptomatic UTI may be prescribed an oral antibiotic by their treating physician. The name and dose (if available) will be documented in the study record. It is up to the participant and/or their caregiver to seek treatment for an active UTI. The study will not provide any medications other than the study products.

Likewise, it is possible that participants might be prescribed an antibiotic for another reason (i.e. not for a UTI). Regardless of the reason, participants will be instructed to pause their daily instillations while undergoing treatment with an antibiotic for any reason. They are then to resume their study treatment upon finishing their outside antibiotic. The participants will document this in their dosing diaries and the information will be maintained in the subject's research records. This issue will also be discussed during the bi-weekly phone calls.

Participants may use non-pharmacologic strategies to help manage their urinary health, such as cranberry juice. The use of these types of treatments will be documented at the study visits, and during the bi-weekly phone calls.

## 7 STUDY INTERVENTION DISCONTINUATION AND PARTICIPANT DISCONTINUATION/WITHDRAWAL

### 7.1 DISCONTINUATION OF STUDY INTERVENTION

Participants may elect to discontinue the study intervention for any number of reasons (not inclusive list): burden of study procedures, side effects, caregiver limitations, etc. They will be educated on signs and symptoms of toxicity (see Section 8.2) and instructed to notify the study team and their physician for advice on discontinuation of study treatment. If a participant develops COVID-19 while participating in this study, the study team will make every effort to keep the participant in the trial. Participants with COVID-19 will remain in the study unless, for medical reasons, they can no longer participate.

Participants will be asked about the reasons for withdrawal from the study when self-initiated.

Regardless of the reason, discontinuation of the study treatment does not mean withdrawal from the study since the study uses an intent –to-treat design. If a participant decides to stop using the study product, and they are willing, they will remain enrolled in the study. This means that study procedures, including bi-weekly phone calls and study visits will go on as scheduled. No drug taper is required when subjects discontinue the study treatment – they may stop immediately. These subjects will also complete the study's final assessments, if willing.

Regarding the discontinuation of treatment, the following information will be documented in the study record:

- Reason for discontinuation of intervention (i.e. treatment).
- Date of last dose.
- Willingness to continue in the study.

If a participant decides to discontinue the study intervention in light of a new or exacerbated clinical finding, we will report the finding on the Adverse Event case report form, and report to the necessary entities as outlined in the Events Reporting Schedule.

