### 1.3 SCHEDULE OF ACTIVITIES (SOA)

Procedures	Screening	Visit 1 (Baseline) 	Visit 2	Visit 3 (Follow-Up Interview)	Optional Post-Intervention Survey
	Day -30 to 0	D0	Day 180±30	Day 90 - 30 / + 90 post-intervention	Day 90 - 30/+365 post-intervention
Medical Record Review	X	X	X	X	
Informed consent		X			
Demographics	X				
Clinical History	X	X	X	X	
Current Medications	X	X	X	X	
Urine Analysis (UA; plus culture if needed) 	X		X		
Pregnancy test	X				
Complete Blood Count		X	X		
Comprehensive Metabolic Panel		X	X		
Self-report measures of QOL 		X	X		
Safety Review 			X		
Every 30 days +/- 2 business days: ship study product		↔			
Schedule bi-weekly phone calls 		↔			
Satisfaction survey 					X

 Participation will commence once eligibility is confirmed via urine analysis (or culture for those individuals with a positive UA); an order for study product will be faxed/mailed to the Research Pharmacy; intervention start date will be the first dose listed on the dosing diary. If the dosing diary is not available, the intervention start date will be recorded as the date told to the study team by the participant and documented in the REDCap database.

 A rapid UA will be performed as part of standard of care at the time of screening; UAs at Visit 2 will be study-paid; positive tests will be followed with a urine culture; test results usually take about 4 days

 QOL measures include the following standardized surveys: Neurogenic Bladder Symptom Score; Neurogenic Bowel Dysfunction Score; SF-Qualiveen; SCI-QOL Measurement System's *Bladder Management Difficulties*, *Bladder Complications*, *Bowel Management Difficulties*, and *Satisfaction with Social Roles and Activities*; and Community Participation Indicators Scale (see Section 8.1, "Efficacy Assessments")

 Study team will make phone calls every two weeks +/- 3 business days to participants throughout the study period to ask about UTIs, adverse events, compliance and general health updates.

 Study team will conduct this visit, likely over the phone, within 30 days after the participant's final instillation in order to assess any adverse events or reactions while the study drug is washing out of the participant's system

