*Confidentiality breach* – The risk of research data or PHI being accessed without study or clinical care need is very low given the standard safeguards used by Michigan Medicine as an institution and by those on the study team. Access to study-related files is granted on the basis of need by the project manager. Electronic files, including electronic consents, are protected by the Michigan Medicine information technology infrastructure, which includes digital encryption, and paper files are stored in a secure environment including locked file cabinets and restricted access offices.

*Toxicity* – The likelihood that a participant in this study would experience toxicity is quite low, as toxicity as a side effect is more associated with high doses of prolonged systemic therapy and/or in patients with impaired renal function. While high doses of gentamicin and similar compounds can be associated with nephro- and ototoxicity, these risks are minimized in this study due to the exclusion of patients with renal impairment and because the systemic absorption via the bladder has been found to be negligible. Using rats, canines and humans, Wan (1994) instilled gentamicin and evaluated serum

levels 30-minutes post-instillation. Only the rat model showed measurable, yet low, non-toxic levels of serum gentamicin; neither canine nor human tests showed any detectable concentration. In studies with limited follow-up data, there were no clinically relevant side effects. While unlikely based on these factors, gentamicin toxicity may manifest in the form of new onset and prolonged numbness, skin tingling, dizziness and vertigo. Other side effects include prolonged muscle twitching, tinnitus, roaring in the ears or hearing loss. Subjects will be instructed to remain well hydrated during study treatment, and to discontinue treatment if they experience any of these symptoms and to contact the study coordinator.

*Overdosage* – Overdosage may increase the risk of toxicity described above. The risk of this is minimal as long as subjects take study treatment as directed. As stated above, the localized dosing is unlikely to cause any increase in serum gentamicin levels and, additionally, the dose of gentamicin in each syringe is far below the threshold at which has been reported to cause adverse reactions.

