## 8.2 SAFETY AND OTHER ASSESSMENTS

- The bi-weekly phone encounters and EMR reviews are the primary means of monitoring the occurrences of side effects and participant tolerability of the Gentamicin treatment. If a participant reports a UTI or UTI symptoms, they will be advised to follow-up with their personal provider for management. Any potential manifestation of gentamicin toxicity will also be assessed during these phone encounters. These include new onset and prolonged numbness, skin tingling, dizziness, and vertigo. They also include prolonged muscle twitching, tinnitus, roaring in the ears or hearing loss. The study team will recommend subjects with these symptoms be seen by a physician for otological assessment and possible study treatment discontinuation.
- A complete blood count and comprehensive metabolic panel will be administered at baseline and six months when treatment is concluded.
- If a study-ordered urine analysis (at screening, and approximately 6-months later, defined here with a window of plus or minus 30 days) reveals an infection, participants will be instructed to follow-up with their personal provider to treat the current infection. The results of the urine test will be included in the EMR and be available to providers across institutions with EPIC access.
- During the follow-up interview (3-months post-treatment), the participant will also be asked if they have used any gentamicin instillations since being off the study drug. If they have used gentamicin, they will be asked if they are still using it. If they have not used gentamicin, they will be asked why not.

- After the follow-up interview, participants will be thanked for their participation in the trial and asked to participate in a final optional survey. If willing, they will be asked about their perceptions of the benefits and/or challenges of using Gentamicin instillations and whether they thought their participation in this trial was worthwhile. This information will be recorded in their CRFs. This option will be offered to participants at the end of their 3-months post-treatment interview and/or at a different time following this interview, depending on their availability and interest in participating.

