## 8.3 ADVERSE EVENTS AND SERIOUS ADVERSE EVENTS

### 8.3.1 DEFINITION OF ADVERSE EVENTS (AE)

This study's definition of AE will align with the FDA definition: "any untoward medical occurrence associated with the use of a drug in humans, whether or not considered drug related." In practice, this means we will consider and document any experience or unfavorable and unintended sign, symptom, or disease that arises while an individual is participating in the study. This interpretation includes positive test results on urine analysis and urine culture (both those provided by the study and those ordered by the participant's treating physician) and reports of UTI symptoms (e.g., malodorous and cloudy urine, fatigue, fever, chills, etc.)

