#### 8.3.4 TIME PERIOD AND FREQUENCY FOR EVENT ASSESSMENT AND FOLLOW-UP

- Study staff will call or otherwise contact participants and/or their caregivers to assess for side effects, adverse events, UTI symptoms, etc. every two weeks for the duration of the study intervention.
  - Staff will ask about changes in health status since enrollment in the study.
  - Study staff will ask directed questions regarding specific side effects or difficulties related to the bladder instillation.
- The reporting period for AEs will begin when the participant signs the main consent and end 30 days after the end of treatment.

---

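### Participants who stop gentamicin early but stay enrolled have their only follow-up blood panel at Day 150 to 210, possibly months after the last dose

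*Protocol*

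**What the plan says.** The Schedule of Activities (Protocol Section 1.3) marks the complete blood count and the comprehensive metabolic panel at Visit 1 and Visit 2 only. Visit 2 is at Day 180 ± 30, so there is one follow-up panel.

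Four places bear on when it is drawn:

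- Section 6.1.1, describing the intervention: "Upon the termination of treatment, they will complete a study visit consisting of a blood draw, urine sample" and quality-of-life measures. The panels are not named here. Reading the blood draw as the count and metabolic panel is an inference from Sections 1.3 and 8.2.
- Section 8.2: "A complete blood count and comprehensive metabolic panel will be administered at baseline and six months when treatment is concluded".
- Section 7.1, on participants who stop the product but remain in the study: "This means that study procedures, including bi-weekly phone calls and study visits will go on as scheduled". They also complete the final assessments if willing. No lab work at discontinuation is mentioned.
- Section 1.3, footnote 5, on the safety review listed in the same Visit 2 column: it takes place "within 30 days after the participant's final instillation in order to assess any adverse events".

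Early stopping is foreseen. Section 2.3.1 tells participants with possible toxicity symptoms "to discontinue treatment if they experience any of these symptoms and to contact the study coordinator". Section 5.3 requires stopping if a barred diuretic is started, and Section 7.1 lists burden, side effects and caregiver limitations as reasons to stop.

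**The concern.** For a full course, the end of dosing and Day 180 are about the same time, and Section 8.2 treats them as one. For someone who stops early they separate, and Section 7.1 keeps the panel at the calendar visit.

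The panel is a safety measure. Section 2.3.1 says that high doses of "gentamicin and similar compounds can be associated with nephro- and ototoxicity". Among the study's own scheduled checks, a renal change without symptoms would show only on this panel. If the panel comes months after the last dose, a transient change may have resolved, and an abnormal value may reflect something that happened since. Some early stoppers will have stopped because of suspected side effects, and for them a timely result is most useful. The protocol already accepts this reasoning for the safety review, which is placed close to the last dose so that it covers the washout of the drug.

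**Working it through.** The plan states no figure for this gap, so there is none to reproduce. The check is day arithmetic.

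**Inputs**
- Visit 2 window: Day 180 ± 30 (Section 1.3), so 180 − 30 = Day 150 to 180 + 30 = Day 210.
- Rule after an early stop: visits stay on schedule (Section 7.1).
- Safety review: within 30 days of the final instillation (Section 1.3, footnote 5).
- s = study day of the last dose, counted on the same clock as Visit 2. The values of s below are assumptions for illustration.

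**Gap from last dose to panel** = (150 − s) to (210 − s) days.

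| Last dose (s) | Earliest panel | Latest panel |
|---|---|---|
| Day 30 | 120 days later | 180 days later |
| Day 60 | 90 | 150 |
| Day 90 | 60 | 120 |
| Day 119 | 31 | 91 |
| Day 120 | 30 | 90 |
| Day 150 | 0 | 60 |

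**When can the scheduled panel fall within 30 days of the last dose?** Only if 150 − s ≤ 30, so s ≥ 120. For every s below 120, all permitted draws come later than that.

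**Comparison with the safety review, s = 90.** The review is due by 90 + 30 = Day 120. The earliest panel is Day 150, which is 30 days after the latest permitted review.

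**Does the panel fall inside the adverse event reporting period?** Section 8.3.4 says: "The reporting period for AEs will begin when the participant signs the main consent and end 30 days after the end of treatment". It does not say whether this means the participant's own last dose or the planned end. For s = 90:
- own last dose: the period ends on 90 + 30 = Day 120, before Day 150, so every permitted panel is outside it;
- planned end at about Day 180: the period ends on about 180 + 30 = Day 210, so every permitted panel is inside it.

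The documents do not settle which applies, so the point does not rest on it.

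**The case against.** A reader might infer that the protocol contradicts itself, with Section 6.1.1 calling for blood at the stop and Sections 1.3, 7.1 and 8.2 calling for it at Day 180. The documents do not support that. Section 6.1.1 describes the planned course and says in the same paragraph that treatment lasts six months. Section 7.1 is the specific rule for people who stop, and it keeps their visits on schedule. Section 8.2 names both anchors in one sentence, and its ± 30 day window belongs to the urine analysis; the window for the panel comes from Section 1.3. So there is a stated rule, and the question is whether it is the best one.

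A reader might also infer that a late abnormal result could not be recorded. Section 8.3.1 points the other way: adverse events include "any experience or unfavorable and unintended sign, symptom, or disease that arises while an individual is participating in the study". The weakness is in timing and attribution, not in recording.

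The other side has further points that stand. Section 2.3.1 describes absorption from the bladder as negligible, and Section 5.2 excludes a documented GFR below 60. Two-weekly contacts and record review (Section 8.1) and referral for symptoms (Section 8.2) can pick up symptomatic events and clinically ordered tests. The toxicity symptoms listed for stopping are neurological and otological, and Section 8.2 already sends those participants to a physician. Someone who starts a barred diuretic may be withdrawn under Section 7.2 and have no later visit. The Manual of Operations (Section 10.1.8) may specify labs at discontinuation, but it was not among the documents reviewed.

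These points lower the stakes. None of them schedules a renal test near the last dose for an early stopper.

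**Conclusion.** The point holds as a low-severity, cheap improvement. Under Section 7.1 as written, anyone who stops for good before Day 120 and stays enrolled has the only follow-up panel more than 30 days after the last dose: 90 to 150 days for a stop on Day 60, and 60 to 120 days for a stop on Day 90. This rests on Section 7.1 governing early stoppers. If site staff instead took Section 6.1.1 literally and drew blood at the stop, the gap would be about zero.

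The documents give no rate of early stopping, so no share of participants can be stated. The expected clinical risk is low. The sample size, the power calculation and the efficacy analyses are not affected.

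**What to change.** Add to Section 7.1 and to the Visit 2 column of the Schedule of Activities: for participants who permanently stop before Day 120 and remain willing, the single post-baseline blood count and metabolic panel is drawn within 30 days after the final instillation, at about the time of the safety review. Section 7.1 already records the date of the last dose and willingness to continue, so the trigger is available. The word permanently keeps pauses during antibiotic courses (Section 6.5.1) from setting it off.

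Leave the rest as it is: the Day 180 questionnaires and urinalysis, the Visit 2 window for everyone else, the two-weekly calls and the adverse event reporting period. In particular, the end of treatment in Section 8.3.4 should not be redefined as the last dose for this purpose. For s = 90 that would fix the end of reporting at Day 120 and rule out the reading that runs to about Day 210, which is 210 − 120 = 90 days longer.

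Cost: wording in two places and the same number of blood draws. These participants make one separate lab trip, because s + 30 falls before Day 150 whenever s is below 120 and the safety review will likely be by phone. They would also have no panel at Day 180. One limit remains: for a last dose on Day 120 or soon after, a draw within 30 days is possible inside the Visit 2 window but not required, and for s = 120 it may still come up to 90 days later.
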